9.2.4 Matching

Not applicable

9.2.5 Baseline Period

This study has no formal baseline period. However, for each eligible and consenting subject, a structured maternal intake telephone interview will be conducted by a trained Research Associate at the Research Center. This interview will include questions on the following: pregnancy history; current health history; pre-pregnancy weight and height; socioeconomic and demographic information including maternal and paternal occupation, education, ethnicity, and income category; current medication use, both

prescriptive and OTC; other environmental or occupational exposures including alcohol, tobacco, caffeine and illicit drug use; current pregnancy complications including illnesses; names and addresses of health care providers; cholesterol test results prior to and during pregnancy; and history of onset and other characteristics of hypercholesterolemia, ASCVD, and/or FH, if applicable (see [Appendix A](#), Forms 02.B. Personal Information Interview Form, 02.B1. Demog Med Hist Interview Form, 02.B2. Cholesterol Study Form, 02.C. Exposure Interview Form).

9.2.6 Study Follow-up

Subjects will be enrolled on an ongoing basis through year 10 of the study and each will be followed from the time they enroll, through the 5-year postnatal follow-up period, for an overall study period of 15 years. Pediatric records will be requested 0-6 weeks after delivery and then on an annual basis. Subjects will be considered lost to follow-up if they have completed the initial intake interview but subsequently fail to complete the outcome interview despite repeated attempts within 1 year of the mother's estimated due date. Voluntary subject withdrawals will be considered separately.

9.3 Variables

9.3.1 Exposure Assessment

The period defining exposure to evolocumab during pregnancy will be any number of days, at any dose, and at any time from the first day of the LMP up to and including the end of pregnancy. Pregnancy will be assessed via maternal report validated by medical records. If the date of the LMP is unclear, or if a first-trimester ultrasound has been done and the estimated date of conception is more than 1 week discrepant from the menstrual period calculation, the first-trimester ultrasound-derived date will be used to calculate a date for LMP and conception.

The period defining non-exposure to evolocumab during pregnancy will be any time within 90 days prior to the first day of the LMP.

9.3.2 Outcome Assessment

9.3.2.1 Primary Outcome

- Rate of major structural **birth** defects, where a major structural **birth** defect will be defined and classified using the CDC coding manual (CDC, 2007). This method has been previously described by the study investigators and the OTIS Research Group (Chambers et al, 2001) and has been used in previous studies conducted by this group.
 - Time Period: Major structural **birth** defects identified up to 1 year of age by the mother, the health care provider, or identified in the dysmorphological examination will be included in the primary analysis. Defects identified after 12 months to 5 years of age will be described and considered separately in the context of a possible pattern.
 - Confirmation: Independent confirmation of certain defects will be required. For example, a heart murmur thought to represent a ventricular septal defect that is ascertained by the examining dysmorphologist will be included if it is confirmed as a heart defect by cardiac ultrasound. Similarly, a midline cutaneous marker at L2-L3 noted in the dysmorphological examination will be included as occult spinal dysraphism only if confirmed by appropriate imaging studies, and in accordance with the CDC coding manual referenced above.
 - Adjudication: A co-Investigator physician with expertise in teratology, pediatrics, and dysmorphology will act as the primary adjudicator of defects classified using the CDC coding system. Verification of classifications in question are performed in 2 ways: (1) by consultation with a Medical Director for the MACDP, who has an ongoing agreement with the MotherToBaby OTIS studies to consult on classification of cases in question, and (2) through a member of the Scientific Advisory Board who has expertise in this area. At annual meetings of the Board, cases classified with major defects are reviewed and where questions arise regarding appropriate classification, primary records are reviewed by one of the members of the Advisory Board with the relevant qualifications.

9.3.2.2 Secondary Outcomes

9.3.2.2.1 Pregnancy Outcomes

- Rate of spontaneous abortion where spontaneous abortion is defined as non-deliberate fetal death which occurs prior to 19 completed weeks post-LMP
- Rate of elective abortion where elective abortion is defined as deliberate termination of pregnancy at any time in gestation
- Rate of stillbirth where stillbirth is defined as non-deliberate fetal death anytime in gestation at or after 19 completed weeks post-LMP
- Rate of premature delivery where premature delivery is defined as live birth prior to 37.0 weeks gestation as counted from LMP (or ultrasound adjusted date)

9.3.2.2.2 Infant Outcomes

- Rate and pattern of minor structural **birth** defects where a minor structural **birth** defect is defined as a structural anomaly (itemized on the study examination form) which has neither cosmetic nor functional significance to the child, and a pattern is defined as the same 3 or more minor structural **birth** defects in 2 or more children (see [Appendix A](#), 04.E. Dymorphology Exam Form). Due to the large variability in the sensitivity and specificity of identification of minor defects, in this study, minor defects are tabulated only in those infants who receive the study-related physical examination. This approach of assessment for clusters is based on prior studies that suggest 3 or more minor malformations is a meaningful cut point ([Leppig et al, 1987](#); [Méhes et al, 1973](#); [Marden et al, 1964](#)).
- Rate of small for gestational age where small for gestational age is defined as birth size (weight, length, or head circumference) \leq 10th centile for sex and gestational age using standard pediatric CDC growth curves for full term or preterm infants ([NCHS, 2000](#); [Olsen et al, 2010](#)).
- Rate of postnatal growth deficiency where postnatal growth deficiency is defined as postnatal size (weight, length, or head circumference) \leq 10th centile for sex and age using standard pediatric growth curves, and adjusted for postnatal age for premature infants if the postnatal measurement is obtained at less than 1 year of age.
- Rate of postnatal serious infections (see [Appendix D](#)) and hospitalizations as assessed throughout the 5-year postnatal follow-up period. Pediatric records will be requested after delivery and then on an annual basis with specific requests for documentation of serious infections and hospitalizations
- Rate of infant reactions to scheduled vaccinations as assessed throughout the 5-year postnatal follow-up period. Pediatric records and a questionnaire regarding vaccine administration according to recommended schedule and any vaccine-related adverse events will be obtained on an annual basis (see [Appendix A](#), 08.12. Vaccine Information Form).
- Infant response to IgG-tetanus antibody as a biological marker to evaluate humoral immune response. To be performed via a heel stick **or venipuncture** and standardized assay test between 6-12 months of age in a subset of infants in each of the study groups, conditional on the consent of the mother.
- Adverse neurodevelopmental outcomes as assessed during 2 periods (between 16 months to 17 months 30 days of age and between 3.5-5 years of age) via standardized tests of performance (further described in [Section 9.4.5](#)).

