9.4.4 Medical Records, Pediatric Evaluations

Upon completion of the outcome interview, each woman will be mailed a packet containing medical records release forms for the delivery hospital, obstetrician (**if the release form has not been received**), pediatrician, internist, cardiologist or other specialty physician if applicable (see [Appendix A](#), Form 09.J. Sample OB Medical Records Release Form). For women whose pregnancies have ended in spontaneous or elective abortion or stillbirth, records release forms will be mailed for the specialty physician's evaluation, if applicable, and if prenatal diagnosis, pathology or autopsy reports are available. Each woman will be asked to sign the forms and to return them along with the **patient** exposure diary. Specific information on maternal cholesterol levels obtained prior to and during pregnancy will be requested for women in the Evolocumab-Exposed group and Comparison Group I.

Upon receipt of the signed medical records release forms, a standard physical evaluation form (see [Appendix A](#), 06.H. Birth Info and Private Pediatrician Form) will be mailed to each pediatrician or other physician responsible for the care of each live born infant. This form includes information on infant size at the time of the latest examination and questions about postnatal complications and congenital anomalies. After delivery, at 1 year of age, and annually thereafter until the child's fifth birthday, a medical records release form for the pediatrician or health care provider caring for the child will be sent to the mother for signature. The signed form along with a standard questionnaire about infant/child growth, congenital malformations, serious infections (see [Appendix D](#) for list of conditions qualifying as serious infection), hospitalizations, and adverse reactions to vaccinations administered is sent to the health care provider (see [Appendix A](#), 07.I. Pediatric One Year Follow-up Form, and 08.I2. Vaccine Information Form).

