9.4.5 Developmental Behavioral Assessments

9.4.5.1 Phase I – Maternal Questionnaires at Infant Age 16 Months to 17 Months 30 Days

The developmental behavioral assessments consist of mail-out questionnaires completed by all mothers/primary caregivers when the child is 16 months to 17 months 30 days of age. The measures are described in [Table 2](#).

All mothers or primary caregivers in each of the 3 study groups will be asked to complete questionnaires about the development of their child when the child is 16 months to 17 months 30 days of age. These scales include the Ages and Stages Questionnaire, the MacArthur-Bates Communicative Development Inventories (CDI), **and the Modified Checklist for Autism in Toddlers (MCHAT-R)** will be mailed when the child is 15 months of age and the mothers or primary caregiver will be asked to complete it when the child is between 16 months and 17 months 30 days of age. The mothers/primary caregivers will also complete 2 questionnaires about their own functioning, the Center for Epidemiological Studies Depression Inventory (**CES-D**), and the Parent Stress Index (**PSI**) Short Form. This will allow for the preliminary evaluation of the child's motor skill, general mental ability, language development, and social and emotional development. Interpretation of these data will be aided by an understanding of the mother's social and emotional adjustment and stress context. Although a window is provided to allow the mother to complete the questionnaires, scoring for these questionnaires is standardized to the month of age of the child so comparisons between groups will appropriately be age-adjusted.

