9.7.2.4.1 Description of Study Enrollment

Outcome	Analysis Subset
Major Structural Birth Defect Among Live Births	All pregnancies ending in at least 1 live born infant
Major Structural Birth Defects Among All Pregnancies Excluding Lost to Follow-Up	All pregnancies excluding lost to follow-up
Spontaneous Abortion	Pregnancies enrolled prior to 20 weeks' gestation
Stillbirth	Pregnancies enrolled excluding lost to follow-up
Preterm Delivery	Pregnancies enrolled prior to 37 completed weeks' gestation, excluding pregnancies ending in twin or higher order multiple births
Minor Structural Birth Defects	Live born infants who have received the dysmorphology examination
Small for Gestational Age Infants	Live born infants excluding twin or higher order multiple births
Breastfeeding	Pregnancies ending in at least 1 live born infant
Postnatal Growth	Live born infants followed up to 1 year postpartum, excluding twin or higher order multiple births
Serious or Opportunistic Infections	Live born infants followed up to 1 year postpartum
Immune Function	Live born infants who received the tetanus titer testing
Response to vaccines	Live born infants who received at least one vaccine
Neurodevelopment	Live born infants for whom developmental screening questionnaires were completed or face-to-face testing was completed

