9.7.2.5.2 Secondary Analysis

The following will comprise the secondary analyses:

1. Comparison of all secondary outcomes between the Specific Evolocumab-Exposed cohort and Comparison Group I
2. Comparison of the primary and all secondary outcomes between the Specific Evolocumab-Exposed cohort and Comparison Group II

The comparison of the prevalence of the total proportion of major structural **birth** defects between the Specific Evolocumab-Exposed cohort and Comparison Group II will be among all live births and, separately, among all pregnancies excluding those lost to follow-up. The comparison of the prevalence of ≥ 3 minor malformations between the Specific Evolocumab-Exposed cohort and each of the 2 comparison groups will be among children who receive the dysmorphological examination. The comparison of IgG-tetanus antibody status (test negative or indeterminate vs test positive) by group (Exposed, Comparison Group I, Comparison Group II) among those in the biological sample sub-study.

In each cohort we will separately calculate the proportion of all pregnancies ending in live birth, spontaneous abortion, stillbirth, elective termination, and lost to follow-up; crude comparisons will be made between cohorts.

The evaluation for a pattern of minor structural **birth** defects will be conducted using the following steps:

1. A comparison among groups of the proportion of infants with any 3 or more minor structural **birth** defects will be made without regard to pattern
2. Among infants with 3 or more minor **structural birth** defects, the Evolocumab-Exposed group will be examined for evidence of a specific pattern of 3 or more defects in any 2 or more children. If such a pattern is identified, Comparison Groups I and II will be evaluated for any evidence of the same pattern.

In each cohort among all live born infants we will separately calculate the proportion of premature delivery, small for gestational age on weight, length or head circumference, and rates of serious infections, hospitalizations, adverse vaccine reactions, and adverse neurodevelopmental outcomes; crude comparisons will be made between cohorts.

Mean birth weight, length and head circumference for full-term live born infants will be compared between cohorts. Postnatal growth parameters will be compared using the proportion of infants ≤ 10 th centile for sex and age with respect to weight, height, or head circumference.

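### The prematurity correction for postnatal growth stops at the first birthday, exactly when the 1-year growth form falls due, which modestly biases a cohort with more preterm births toward apparent growth deficiency

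*Protocol*

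**What the plan says.** Section 9.3.2.2.2 defines postnatal growth deficiency as weight, length or head circumference at or below the 10th centile for sex and age, "adjusted for postnatal age for premature infants if the postnatal measurement is obtained at less than 1 year of age". The abstract repeats the under-1-year limit.

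Table 1 places the paediatric growth questionnaire only in the column for yearly contact from 1 to 5 years. Section 9.4.4 has the records release and questionnaire sent "After delivery, at 1 year of age, and annually thereafter until the child's fifth birthday". A separate physician form follows receipt of the signed releases after the outcome interview: "This form includes information on infant size at the time of the latest examination".

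The growth subset in section 9.7.2.4.1 is "Live born infants followed up to 1 year postpartum, excluding twin or higher order multiple births". Section 9.7.2.5.2 gives the comparison: "Postnatal growth parameters will be compared using the proportion of infants" at or below the 10th centile.

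For the questionnaires at 16 months to 17 months 30 days, section 9.4.5.1 says that "scoring for these questionnaires is standardized to the month of age of the child so comparisons between groups will appropriately be age-adjusted". The neurodevelopment subset is "Live born infants for whom developmental screening questionnaires were completed or face-to-face testing was completed", so neither preterm children nor multiples are excluded.

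**The concern.** The protocol accepts that a preterm infant must be compared with infants of the same corrected age, and then withdraws that correction at the age when the scheduled growth measurement is taken. Two things follow.

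- Visit timing decides classification. Two preterm infants of identical size and gestation, seen two weeks apart around the first birthday, can fall on opposite sides of the 10th centile.
- Prematurity leaks into the growth outcome. Preterm delivery is a separate secondary outcome, and it may differ between cohorts. Table 3 footnote h cites rates of 16.1% and 6.2% from two sources. Section 9.9 expects exposed women to be more severely diseased than Comparison Group I. Comparison Group II does not have the disease at all. If exposed women deliver preterm more often, part of that difference reappears as growth deficiency and points toward drug harm.

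Section 9.7.2.5.2 plans adjusted comparisons, but neither gestational age nor prematurity is named among the adjustment variables.

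**Working it through.** **1. The plan's own figure.** Table 3 gives 82% power for postnatal growth deficiency with 46 v 108 infants, a 10% baseline rate and a relative risk (RR) of 2.8 (28% v 10%), two-sided alpha 0.05.

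- Pooled rate = (46 × 0.28 + 108 × 0.10)/154 = 0.1538.
- Pooled standard error = √[0.1538 × 0.8462 × (1/46 + 1/108)] = 0.0635.
- Power with that standard error under both hypotheses = Φ(0.18/0.0635 − 1.96) = 80.9%, close to the stated 82%.
- The usual form, pooled under the null and unpooled under the alternative, gives 77.9%; Fisher's exact test gives 73.6%.

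The point does not depend on this figure. It serves only as the yardstick of RR 2.8.

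**2. Age error from chronological age** (40-week reference assumed). Offset in months = (40 − weeks at birth) × 7/30.44.

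| Weeks at birth | Offset (months) | Share of 12 months |
|---|---|---|
| 36 | 0.9 | 8% |
| 34 | 1.4 | 11% |
| 32 | 1.8 | 15% |
| 28 | 2.8 | 23% |

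**3. Bias model.** Inputs:

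- Preterm rate: 9% in the comparison group and 9% × 2.8 = 25.2% in the exposed cohort (Table 3, preterm row).
- No true growth effect: 10% of correctly aged infants lie at or below the 10th centile (z = −1.2816).
- Uncorrected age moves preterm infants down by s SD. The protocol gives no value; s = 0.2 to 0.8 is an assumption.
- Every preterm infant is measured at or after 12 months, so none is corrected. This is the worst case.

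Formulas:

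- Rate in uncorrected preterm infants: r = Φ(−1.2816 + s).
- Exposed rate = 0.748 × 10% + 0.252 × r.
- Comparison rate = 0.91 × 10% + 0.09 × r.

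| s (SD) | r | Exposed | Comparison | Spurious RR |
|---|---|---|---|---|
| 0.2 | 14.0% | 11.0% | 10.4% | 1.06 |
| 0.4 | 18.9% | 12.2% | 10.8% | 1.13 |
| 0.6 | 24.8% | 13.7% | 11.3% | 1.21 |
| 0.8 | 31.5% | 15.4% | 11.9% | 1.29 |

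For s = 0.8: exposed 0.0748 + 0.252 × 0.315 = 0.154; comparison 0.091 + 0.09 × 0.315 = 0.119; ratio 1.29. With a wider assumed range of s = 0.25 to 1.0 the spurious RR is 1.08 to 1.37.

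**4. Milder conditions.**

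- Smaller preterm difference: at a preterm RR of 1.5 to 2.0, over s = 0.25 to 1.0, the spurious RR is 1.02 to 1.21.
- Half of the preterm infants measured before 12 months (an illustration): the preterm rate becomes 10% + 0.5 × (r − 10%). At s = 0.8 this is 20.75%. Exposed = 0.0748 + 0.252 × 0.2075 = 12.7%; comparison = 0.091 + 0.09 × 0.2075 = 11.0%; RR 1.16. At s = 0.2 the RR is 1.03.

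**5. Chance of a false signal.** At 46 v 108 and the full preterm RR of 2.8, the chance of a significant excess from this artefact alone is about 4% to 13% over s = 0.25 to 1.0, against 2.5% in that direction with no effect. Counting a child as deficient on any of the three measurements (assumed correlation 0.3 to 0.7) gives RR 1.07 to 1.28 and a chance of 4% to 15%.

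**6. After the fix.** With corrected age also used at the 1-year form, r returns to 10% in both cohorts and the spurious RR is 1.00.

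**The case against.** The strongest reply is that the effect is small and that its size depends on stacked assumptions. The SD shift has no anchor in the protocol. Preterm rates of 9% v 25.2% are a power-calculation scenario, not an expectation. Some measurements will be corrected after all: the post-delivery physician form records size at the latest examination, which can precede the first birthday. The growth subset excludes multiples. The 12-month rule is prespecified and identical in every cohort, and preterm delivery is reported beside growth, so an imbalance would be visible. All of this stands and limits the size. It does not remove the fault, because an identical rule still acts unequally when preterm rates differ, and the scheduled form still falls on the cut-off.

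A reader might infer that a cohort with more preterm births will plainly look growth-deficient. The figures do not support that: a spurious RR of about 1.0 to 1.4 is far below the detectable 2.8.

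A reader might also infer that the 16-17 month questionnaires are scored at chronological age, so that preterm children will look delayed. The protocol does not say so. It specifies month of age without stating whether that age is corrected, and this detail may properly sit in the SAP or the instrument manuals. What remains is that section 9.4.5.1 asserts suitable age adjustment, which holds for preterm children only if corrected age is used. That calls for confirmation and is not an error shown in the document. Even if age were uncorrected, a continuous score would move the cohort mean by only 0.04 to 0.16 SD (s = 0.25 to 1.0 times 0.252 − 0.09 = 0.162), against the 0.5 SD that Table 3 gives for Phase II.

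**Conclusion.** The point holds for growth. The protocol fixes an explicit correction limit that coincides with its main scheduled growth measurement, so correction of a preterm infant depends on which side of the birthday the visit falls. If the exposed cohort has more preterm births, the bias is toward apparent harm. It is modest: a spurious RR of about 1.06 to 1.29, given preterm rates of 9% v 25.2%, an assumed shift of 0.2 to 0.8 SD and no preterm infant corrected, and less under milder conditions. If preterm rates are equal, no difference between cohorts arises from this source, though classification near 12 months remains arbitrary. For the questionnaires it is a request for clarification only. The primary outcome is untouched. The change is worth making because it is cheap and removes the artefact, not because the artefact threatens the study's main conclusion.

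**What to change.** - **Section 9.3.2.2.2 (and the abstract):** apply gestation-corrected age to every growth measurement used in the analysis, through and including the 1-year form. If an upper age limit is kept, set it between scheduled forms and give the reason for it. The protocol offers no basis for a particular limit, and 24 months would coincide with the 2-year form.
- **Sensitivity analysis:** report growth deficiency in term-born infants separately.
- **Section 9.4.5.1:** confirm that the 16-17 month questionnaires are scored by corrected age, or point to the document that settles it.

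**Cost:** wording and one date calculation. Delivery date (section 9.4.3) and LMP or first-trimester ultrasound dating (section 9.3.1) are already collected. The downside is small: a few very preterm children may need a younger questionnaire norm.
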